3.2 Procedures

Magnetic Resonance Imaging (MRI): An MRI scan (without contrast) of the bilateral thigh and calf muscles will be performed to characterize the pattern of muscle involvement and evaluate the muscle fat fraction (MFF). Three-point Dixon MRI of leg muscles will be performed to generate fat fraction (FF) maps as described in the detailed CMT47 Imaging protocol. All MR imaging will be supervised by an attending pediatric neuroradiologist to ensure acquisition of complete, high-quality scans. MR imaging will be acquired at baseline and at multiple time points. The data will be transferred to a central site for quality control and analysis.

Nerve Conduction Study (NCS): NCS is an electrophysiological test to evaluate the sensory and motor responses in the upper and lower extremities. The specific measurements include distal latency, amplitude and conduction velocity. Serial measurements can show progression of the disease, as in axonal and demyelinating conditions. Ideally, NCS will be performed on the left arm and left leg. The same limbs will be assessed at every visit. The following nerves will be studied: median motor, radial sensory and peroneal motor response at the extensor digitorum brevis (EDB) and the tibialis anterior (TA).

Pulmonary Function Test, sitting and lying (PFT): The primary purpose of pulmonary function testing is to identify the severity and progression of pulmonary impairment. The specific measurements are lung volumes (Forced Vital Capacity-FVC, Forced Expiratory Volume-FEV and Forced Expiratory Flow-FEF) and maximal respiratory pressures (inspiratory and expiratory). PFTs will be performed in subjects older than 5 years of age based on the evaluator's assessment of subject's compliance and/or ability to follow instructions. The evaluator should complete the seated PFT prior to the supine PFT.

Scoliosis Series X-ray: The scoliosis X-ray includes the thoracic spine (upper back) and the lumbar spine (lower back). The scoliosis X-ray will not be completed on subjects older than 17 years of age.

Pregnancy Test- (individuals of childbearing potential only) Urine pregnancy test for females of childbearing potential (Subject has experienced onset of menses and is not postmenopausal) will be collected. Results of urine pregnancy test must be reviewed and confirmed to be negative prior to

proceeding with any assessments involving radiation. If a urine pregnancy test is positive, it must be confirmed by a serum pregnancy test. If the subject's urine or serum pregnancy test is positive, assessments involving radiation should not be performed.

3.3 Skin Biopsy (Optional)

An optional skin sample will be taken for exploratory research purposes. If the participant consents, the neurologist will take a small skin sample via punch biopsy (approximately 3-4mm). Lidocaine cream will may be applied 30 mins prior to the area to be biopsied to anesthetize the skin. The skin sample will be sent to specialized laboratory for fibroblast culturing and subsequently the participants fibroblasts will be stored for future use.

3.4 Subject Withdrawal

Subjects may be withdrawn from the study for any of the following reasons:

- Withdrawal of the informed consent
- Lost to follow-up
- Withdrawal at the investigator's discretion

Subjects should be withdrawn at any time if the investigator concludes that it would be in the subjects' best interest for any reason. Subjects may voluntarily withdraw from the study for any reason at any time. They may be considered withdrawn if they state an intention to withdraw, or fail to return for visits, or become lost to follow up for any other reason. Protocol deviations should not lead to subject withdrawal unless they indicate a significant risk to the subject's safety. If premature subject withdrawal occurs for any reason, the investigator must determine the primary reason for a subject's premature withdrawal from the study and record this information on the case report form (CRF). For subjects who are lost to follow-up (i.e., those subjects whose status is unclear because they fail to appear for study visits without stating an intention to withdraw), the investigator should show due diligence by documenting in the source documents steps taken to contact the subject, e.g., dates of telephone calls, registered letters, etc. In the case of death, a subject will be considered withdrawn.

Subjects who terminate from the study prior to Visit 3, if they agree, will undergo an early termination/end of study visit if possible. The early termination/end of study visit is comprised of the Visit 3 assessments. Subjects can voluntarily withdraw from participation in this research study at any time. They may also request that their information be removed and destroyed from the study and that their data not be used in the analysis, evaluation or publication of this research study. That request would need to be in a written format, directed and submitted to the Principal Investigator.

3.5 Unscheduled Visit(s)

Subjects who experience any serious adverse effects (per21cFR312.32) or severe adverse events (CTCA>grade3) or experience another event of concern to the site Principal Investigator can be scheduled for an additional visit for further evaluation. If an unscheduled visit occurs, a member of the clinical study team (PI, sub-investigator, nurse coordinator, or clinical nurse) will evaluate the subject to determine the cause of the visit and provide care as needed. All procedures and/or sample collections should be documented within in unscheduled visit CRF.

4 POTENTIAL RISKS

Medical History and Record Review: There may be psychological distress associated with providing medical and family history. Frequent breaks or even cessation of the interview may be taken to reduce

risk of distress. There is a risk of potential loss of confidentiality and personal health information. Every effort will be made to keep the subject's information confidential; however, this cannot be guaranteed.

Physical and Neurological Examination: There is a small risk of mild pain or discomfort from positioning, activities, equipment, and procedures for the neurologic examination.

Neuropsychological Tests and Quality of Life Measures: These tests do not involve any medical procedures and have no inherent risks. However, subjects may experience mild frustration or nervousness due to cognitively challenging tasks. Subjects and parents may experience mild levels of psychological discomfort when completing rating forms on topics including school performance, mood, and quality of life.

NCS: Electrical stimulation may cause muscle contraction that may be uncomfortable. Also, there may be mild muscle soreness after muscle testing. This may last for one to two days. Subjects may experience some slight discomfort from having to lay or sit still during the procedure.

MRI: Subjects are at risk for injury from the MRI magnet if they have pacemakers or other implanted electrical devices, brain stimulators, some types of dental implants, aneurysm clips, metallic prostheses, permanent eyeliners, implanted delivery pump, or shrapnel fragments. Welders and metal workers are also at risk for injury because of possible small metal fragments in the eye of which they may be unaware. Individuals will be screened for these conditions and implants before having any scan, and if they have any, they will not receive an MRI scan (or per the clinical judgement of a certified radiologist and radiology staff, may have a modified MRI that is deemed safe). In addition, all magnetic objects must be removed before entering the MRI scan room. We do not plan to administer gadolinium contrast as part of this imaging protocol.

Subjects with fear of confined spaces may become anxious during an MRI. Those with back problems or significant contractures may have pain or discomfort from lying in the scanner. The noise from the scanner is loud enough to damage hearing. Everyone having an MRI scan will be fitted with hearing protection. There are no known long-term risks of MRI scans.

X-Ray: This is a relatively painless and safe study. Subjects are exposed to a minimal amount of radiation during the scoliosis series X-ray to create detailed images of the spine.

Pulmonary Function Tests: There are no known risks. Subjects may feel tired after the procedure due to the respiratory effort.

Physical therapy assessments: The outcome measures (CMTPedS and CMTNSv2) carry a very small risk of mild pain, fatigue or discomfort from positioning, activities and equipment.

Blood collection: Subjects may experience minor pain and bruising during routine phlebotomy. All proper precautions will be taken, and only qualified individuals will perform blood draws.

Loss of confidentiality: There is a risk that confidentiality may be breached during the study. These risks are mitigated by anonymizing data and using secure servers and databases. If there is a confidentiality or data breach, the subject will be informed as soon as it is discovered.

Unforeseen risks: A previously unknown problem could result from participation in this observational study. It is not possible to estimate the chance of such problems or how serious problems could be.

| Procedures and Risks | Description | Risk | Mitigation measures |
|--|---|--|---|
| Neurology Clinic Visit | Vital signs, anthropometrics, history of present illness and interim information will be obtained. Physical examination including general, neurological exam (including MMT) and hand-held dynamometry | Discomfort or psychological stress. | Subjects allowed to take breaks. |
| CMT Specific Scales 
 - CMTPedS for subjects 5-17 years of age - CMTInfs < 4 years of age - CMTNSv2 for subjects >18 years of age - CMT-FOM for subjects > 18 years of age - CMT Health Index (CMTHI) for >18 years of age | Validated clinical outcome measures to monitor progression of sensorimotor function, disease-burden and quality of life in CMT subjects | No known risks. May experience mild frustration or fatigue with challenging tasks. May experience mild psychological discomfort when completing rating forms on topics including school performance, mood, and quality of life. | Subjects allowed to take breaks. |
| Electrophysiology Nerve Conduction Studies (NCS) | Evaluates sensory and motor responses in the upper and lower extremities including distal latency, amplitude and conduction velocity. | Risk of discomfort with muscle contraction from stimulation. Mild muscle soreness and fatigue. Discomfort from staying still during the procedure. | Procedure expectations will be communicated with the subjects and time will be given between stimulations. |
| Magnetic Resonance Imaging of the thigh and calf muscle without contrast | MRI scan of the thigh and calf muscle to characterize the structural abnormalities in CMT4J. | Risk for injury from the MRI magnet if present: pacemakers or other implanted electrical devices, brain stimulators, some dental implants, aneurysm clips, metallic prostheses, permanent eyeliner, implanted delivery pump, magnetic devices (such as | Individuals are screened to ensure MRI safety procedures are met before a scan Hearing protection for risk of hearing damage |
| Brain MRI without contrast | MRI scan of the brain. | | |

| | | | |
|---|--|---|--|
| | | magnetic spine growing rods) or shrapnel fragments. Risk of discomfort from laying on hard surface or anxiety if fear of confined spaces or loud noises | |
| Neuropsychological and Physical therapy Assessments | A series of performance-based activities to assess psychomotor functioning and quality of life. This includes: 
 • Vineland Adaptive Behavioral Scale • PEDICAT • PedsQL • ONLS • pCMT-QOL • Bayley-III, • WASI-II, WPPSI-IV • Stanford-Binet test V • TUG | Discomfort or psychological stress and tiredness. | Subjects allowed to take breaks. |
| Pulmonary Function Tests (PFTs) | PFTs to identify severity and progression of pulmonary dysfunction. Lung volume measurements: Forced Vital Capacity-FVC, Forced Expiratory Volume-FEV, and Forced Expiratory Flow-FEF. Pressure Measurements: maximal inspiratory and expiratory. | No known risks. May feel tired after the procedure. | Subjects allowed to take breaks. |
| Scoliosis series X-ray | Scoliosis series X-ray includes the thoracic spine (upper back) and the lumbar spine (lower back) to identify areas of spine curvature. | Exposure to minimal amount of radiation. | Adherence to the minimum exposure to radiation as permissible. |
| Blood collection | Exploratory blood draw | Minor pain and bruising | Adherence to maximum blood volumes permitted in |

| | | | |
|------------------------|---|---|--|
| | | | pediatric subjects |
| Skin biopsy (optional) | Small punch biopsy for future exploratory use | Exposure to lidocaine cream and a small irritation to the skin for the punch biopsy | Only trained individuals can perform a skin biopsy |

5 SUBJECT SAFETY AND DATA MONITORING

This study will not involve an investigational drug and does not require a DSMB.

Clinical data collected will be entered into a 21CFR11-compliant database by each study site. CRFs will be associated with each scheduled visit and all protocol-related research assessments.

As part of the consent process, subjects will be informed that their de-identified data will be shared with various third parties, including Regulatory Authorities, IRBs or other academic researchers and collaborating biotechnology companies without future consent requests. Future use of data and samples, including sharing with third parties (e.g., regulatory authorities), will be governed by each site's local informed consent form.

6 PROCEDURES TO MAINTAIN CONFIDENTIALITY

Subjects enrolled in the natural history study will be given a unique identifier that includes the project (disease), a site number that corresponds to the site, and a sequentially assigned subject number (ex: CMT4J-001-001).

Collaboration with other institutions and/or researchers may occur. In this case, all subject information shared with collaborators will be de-identified. Identifiable information may be shared with other studies if approved by the IRB or other regulatory body.

Study records are confidential, and they will be kept in a secure environment and protected to the full extent of the law.

The study monitor, representatives of the Institutional Review Board (IRB), and/or regulatory agencies may inspect all documents and records required to be maintained by the site Principal Investigators, including but not limited to, medical records (office, clinic, or hospital) and pharmacy records for the participants in this study. The clinical study sites will permit access to such records.

The study participant's contact information will be securely stored at each clinical site for internal use during the study. At the end of the study, all records will continue to be kept in a secure location for as long a period as dictated by the reviewing IRB, Institutional policies, or sponsor requirements.

Study participant research data, which is for purposes of statistical analysis and scientific reporting, will be transmitted to and stored within an electronic data capture system which is 21 CFR11 compliant. The electronic case report form will not include the participant's contact or identifying information. Rather, individual participants and their research data will be identified by a unique study identification number.

7 POTENTIAL BENEFITS

Participation in this research study may not provide a direct benefit to participants. This study may expand our knowledge about the genotype range and phenotypic expression of CMT4J. It will also

yield information about other system involvement and the frequency of this in the CMT4J/FIG4 population. The long-term objective is to be able to provide information about natural history and outcome measure validity, which is essential for future therapeutic clinical trials.

8 PROTOCOL DEVIATIONS

A major protocol deviation is a deviation that may adversely affect the rights, safety or well-being of the subjects and/or the quality and integrity of data or may affect the subject's willingness to have consented in the study. "May" in this paragraph refers to a "reasonable possibility" of having such an effect; it does not require that such an effect has unequivocally occurred.

Major protocol deviations include but are not limited to: enrolment of ineligible subjects, factors that may confound measurement or interpretation of key outcome measures (e.g., a final study endpoint or several smaller "during study" outcome measures), safety or efficacy assessments not performed, or a pattern or frequency of "minor" deviations that together meet criteria described herein for a major deviation.

A minor protocol deviation is a deviation that is unlikely to adversely affect the rights, safety or well-being of the subjects and/or the compromise the quality and integrity of data or affect the subject's willingness to participate in the study. An example of a minor protocol deviation would be a missed laboratory test or a missed study visit.

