2.5.2 Handling of Subject Withdrawals or Termination

Every effort will be made to undertake protocol-specified safety follow-up procedures to capture protocol specified assessments. An investigator may discontinue or withdraw a participant from the study for the following reasons:

- Significant non-compliance
- If the participant meets an exclusion criterion (either newly developed or not previously recognized) that precludes further study participation
- Subject has completed the study follow-up period
- Death
- Screening Failure

The reason for participant discontinuation or withdrawal from the study will be recorded on the discontinuation/withdrawal Case Report Form (CRF).

A participant will be considered lost to follow-up if a follow up visit is missed and the participant is unable to be contacted by the study site staff following at least three attempts (where possible, three telephone calls and, if necessary, a certified letter to the participant's last known mailing address or local equivalent methods).

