3 STUDY PROCEDURES AND SCHEDULE

The frequency of the following assessments will be according to the schedule of study procedures in Appendix 1. Not all the following assessments need to be performed at every visit, only those that the subject is able to perform.

1. 4.1 Medical Information

Medical History: Medical history of participating subjects will be recorded in order to obtain the following data: basic demographic information (sex, ethnicity), past medical history, birth history, surgical history, developmental history, medications and family history. We will also collect time of symptoms onset (e.g., motor, language, etc.) and progression, age at diagnosis and genetic results.

Physical and Neurological Examination: At each visit, a physical exam will be recorded including but not limited to evaluation of the ears, nose, throat, heart, lungs, abdomen, back, and extremities, motor and sensory, and vital signs which will include blood pressure (measured in one arm or, if necessary, one leg, after the subject has been seated for approximately 5 minutes), pulse, temperature, height, weight, and head circumference.

A detailed neurological examination including but not limited to evaluation of cranial nerves, muscle tone, muscle strength, sensation, gait, coordination and deep tendon reflex testing will also be performed. Handheld dynamometry will also be performed during clinic visits in muscles of the upper and lower extremities. The examination is anticipated to take approximately 30 minutes.

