Stanford-Binet Fifth Edition (SB5): The Stanford-Binet test V is an examination meant to gauge intelligence through five factors of cognitive ability. These five factors include fluid reasoning, knowledge, quantitative reasoning, visual-spatial processing and working memory. Both verbal and nonverbal responses are measured. Each of the five factors is given a weight and the combined score is often reduced to a ratio known commonly as the intelligence quotient, or IQ. For children ages 2 to 5, use the early SB5.

Timed Up & Go Test (TUG): The Timed Up and Go Test (TUG) is a measure of mobility. Patients are asked to sit in a regular chair and upon command rise from the chair, walk at their normal pace to a line on the floor 10 feet (3 meters) away from the chair, return to the chair and sit down again. The time required by the patient to complete the assessment is measured and recorded. The TUG should be performed in triplicate at each visit and the best performance will be used for analyses. The TUG is administered by a Physician, a Physical Therapist, or designee familiar with the test. Every attempt should be made that the same assessor is administering the TUG in a given patient throughout the study. TUG will be administered to ambulatory patients in this Study.

Pediatric Evaluation of Disability Inventory-Computer Adaptive Test (PEDICAT): PEDI, originally published in 1992 by Haley et al. and revised as a computer adaptive test (CAT) – the PEDI-CAT, is a parent/clinician functional test that measures abilities in 4 content domains: daily activities, mobility, social/cognitive, responsibility. It will be completed by the caregiver with support from a qualified study center staff, for subjects younger than 20 years of age (9).

Pediatric Quality of Life Inventory (PedsQL)-Family Impact Module: Measures parent self-reported physical, emotional, social, and cognitive functioning, communication, and worry (10). The Module

also measures parent-reported family daily activities and family relationships. This assessment will be used in subjects between 2 and 18 years of age.

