APPENDIX 1: SCHEDULE OF EVENTS

| Study Day | Screening | Baseline | Month 12 | Month 24 |
|---|------------------|------------------|------------------|------------------|
| Windows | | (± 4 wks) | (± 4 wks) | (± 4 wks) |
| Informed Consent | X | | | |
| Medical Information | | X | X | X |
| Demographics | | | | |
| Medical History | | X | X | X |
| Family History | | X | | |
| CMT4J Diagnosis and History | | X | | |
| Clinical Procedures | | | | |
| Inclusion/Exclusion Criteria | X | | | |
| Vital Signs ^a | | X | X | X |
| Height and Weight | | X | X | X |
| Physical Exam ^b | | X | X | X |
| Neurological Exam ^c | | X | X | X |
| Urine Pregnancy (for female subjects) ^d | | X | X | X |
| Blood Collection for Future Exploratory Analysis ^e | | X | X | X |
| Skin biopsy (optional, any visit, only once) | | X | X | X |
| Adverse Events | | X | X | X |
| Concomitant Medications | | X | X | X |
| CMT Scales* | | | | |
| CMTpedS ^f | X | X | X | X |
| CMTInfS ^g | X | X | X | X |
| CMTNSv2 ^h | X | X | X | X |
| CMT-FOM ^h | X | X | X | X |
| CMT Health Index (CMTHI) ^h | X | X | X | X |
| Clinical Studies | | | | |
| Thigh and Calf MRI without contrast | | X | X | X |
| Brain MRI without contrast | | X | X | X |
| Nerve Conduction Study (NCS) ⁱ | | X | X | X |
| Pulmonary Function Test (PFT) ^j | | X | X | X |
| Scoliosis Series X-ray ^k | | X | X | X |
| Neuropsychological and Physical Therapy Assessments | | | | |
| Vineland Adaptive Behavior Scale | | X | X | X |
| PEDICAT ^l | | X | X | X |
| Bailey III | | X | X | X |
| WASI-II or WPPSI-IV | | X | X | X |
| Stanford Binet – V | | X | X | X |
| Timed up and go (TUG) | | X | X | X |
| Wearable devices | X | X | X | X |
| Questionnaires | | | | |
| PedsQL ^m | | X | X | X |
| Overall Neuropathy Limitation Scale (ONLS) (18 years and older) | | X | X | X |
| pCMT-QOL PRO (8 to 18 years) | | X | X | X |
| pCMT-QOL (8 to 18 years parent-proxy) | | X | X | X |
| pCMT-QOL (0 to 7 years parent-proxy) | | X | X | X |

-
- ^a Temperature, pulse, blood pressure measured in one arm or leg after the patient has been seated for ~ 5 minutes.
 - ^b Exam of heart, lungs, abdomen, back, and extremities; height and weight; head circumference
 - ^c Includes evaluation of cranial nerves, muscle tone, muscle strength, sensation, gait, coordination and deep tendon reflex testing, handheld dynamometry

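### Does the overlap between a missed visit (minor) and assessments not performed (major) require a change to the protocol?

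*Protocol*

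**What the plan says.** Protocol Section 8 sets the major grade by consequence: "A major protocol deviation is a deviation that may adversely affect the rights, safety or well-being of the subjects and/or the quality and integrity of" the study's data. It explains that a realistic chance of such an effect is enough and that the effect need not have occurred. An open-ended list of major deviations follows. It includes "safety or efficacy assessments not performed", factors that could confound key outcome measures (a final endpoint is one example), and a run of minor deviations that together reach the major standard. A minor deviation is one unlikely to have these effects, and the section adds: "An example of a minor protocol deviation would be a missed laboratory test or a missed study visit".

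Other sections bear on which omissions are deviations at all. Section 3 says: "Not all the following assessments need to be performed at every visit, only those that the subject is able to perform". For the TUG, Section 3.1 says: "TUG will be administered to ambulatory patients in this Study". Appendix 1 schedules the TUG at Baseline, Month 12 and Month 24, with no footnote on walking ability.

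On reasons for absence, Section 2.5.2 says: "The reason for participant discontinuation or withdrawal from the study will be recorded", and names a case report form for it. Section 3.4 says of subjects: "They may be considered withdrawn if they state an intention to withdraw, or fail to return for visits". Section 10 gives a sample size of about 20 without a formal calculation and calls all analysis exploratory.

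**The concern.** Two things look wrong.

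First, a missed visit appears to belong to both grades. When a subject does not attend, the vital signs, examinations and outcome measures scheduled for that visit are not done, which matches the major list; yet the visit itself is named as a minor example. Read literally, the ranking can even be inverted: one test skipped at an attended visit could be major while the loss of the whole visit is minor. The initial period has only two follow-up visits, so it is also hard to call the loss of one unlikely to affect the data. Four sites could log the same event differently.

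Second, Section 8 makes no exception for a test the subject can no longer do. If a TUG omitted after loss of walking were logged as major at one site and as expected at another, the deviation record could not show consistently which outcome data are absent because of the disease. In a natural history study that distinction matters.

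**Working it through.** The protocol gives no figure to reproduce on this point. The check sets the sections side by side and then sizes what is at stake.

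**1. Do the two examples in Section 8 collide?** Yes. Assessments not performed are major, a missed visit is minor, and a missed visit consists of assessments not performed. The clause that escalates a pattern of minor deviations concerns repetition and does not place a single missed visit.

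**2. Does the rest of Section 8 help?** Largely. Both lists are illustrative, and the governing test is the likely effect on subjects or data. A missed Month 24 visit can be graded major by that test, or as a matter affecting a final endpoint. An isolated missed Month 12 visit can reasonably be graded minor. The wording also looks carried over from an interventional template: it speaks of efficacy in a study without a product, and the adverse event definition in Section 9.1 refers to an investigational vaccine. That is an inference, but it fits a clerical slip better than a deliberate rule.

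**3. Is a TUG omitted for loss of walking a deviation?** No. Section 3 requires only what the subject is able to perform, and Section 3.1 restricts the test to ambulatory patients. The omission follows the protocol, and Section 8 grades only departures from it. The absent footnote in Appendix 1 is a cross-reference point, since Section 3.1 carries the restriction.

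**4. Is the reason for absence lost?**
- At an attended visit, walking ability would usually be visible from the gait examination, the medical history, PEDICAT mobility (under 20 years) or ONLS (18 and older).
- A subject who stops attending can be treated as withdrawn, and a reason is then recorded.
- The gap is mainly a subject who misses Month 12 and returns. A reason-not-done item for that case is case report form content. Section 5 links those forms to each scheduled visit and assessment; they are not shown.

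**5. What does a missed visit cost?** Outcome rows in Appendix 1 at each of Month 12 and Month 24:
- CMT scales 5 + clinical studies 5 + neuropsychological, physical therapy and wearable rows 7 + questionnaires 5 = 22.
- Applicable at age 25: CMTNSv2, CMT-FOM, CMTHI, two MRI rows, NCS, PFT, Vineland (if a suitable caregiver is present), WASI-II, SB5, TUG, wearable, ONLS = 13.
- Applicable at age 10: CMTPedS, two MRI rows, NCS, PFT, scoliosis X-ray, Vineland, PEDICAT, WASI-II/WPPSI-IV, SB5, TUG, wearable, PedsQL, pCMT-QOL self-report, pCMT-QOL proxy = 15.
- One missed follow-up visit: 1/2 = 50% of that subject's scheduled post-baseline visits in the initial period; with 20 subjects, 1/(20 × 2) = 1/40 = 2.5% of all planned post-baseline subject-visits.

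For one subject's linear slope, assuming equal independent residual variance s² (the protocol specifies no such model), the variance is s² / Σ(t − t̄)²:

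| Visits attended (years) | Σ(t − t̄)² | Slope variance | SE ratio to full schedule |
|---|---|---|---|
| 0, 1, 2 | 2 | 0.5 s² | 1.0 |
| 0, 2 | 2 | 0.5 s² | 1.0 |
| 0, 1 | 0.5 | 2.0 s² | √(2.0/0.5) = 2.0 |

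Missing Month 12 leaves this precision unchanged; missing Month 24 doubles the standard error.

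**6. Does the label alter any of this?** No. The counts and ratios in step 5 describe data lost through non-attendance, whichever class is logged. The protocol links the class to no analysis set, exclusion or estimate, and a class does not record why data are absent.

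**The case for a change.** The strongest case for a change is that this is a wrong statement in the protocol and not a detail left to the analysis plan. Sites log against Section 8, and one sentence would settle it: drop the visit from the minor example, or say when a visit not made up within the 4-week window counts as assessments not performed. The text should not rank the loss of a whole visit below one skipped test, least of all with about 20 subjects and two follow-up visits.

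The inconsistency itself stands. So does the remark that efficacy has no defined meaning here, which leaves unclear which omissions that item covers.

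The rest is weaker. The ranking need not be inverted, because the data-integrity test already allows a missed Month 24 visit to be major. Nor are all safety data necessarily lost with a visit: Section 9.3.1 collects adverse events from consent to the end of study, by routes that include unsolicited complaints. The count of two follow-up visits covers only the initial period, since the synopsis allows extension up to 60 months if feasible. Which class a missed visit deserves is partly preference, and moving all of them to major has a cost: more major deviations logged, including Month 12 absences that cost the slope in the working nothing.

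**Conclusion.** No change to the plan follows. Section 8 does allow a single missed visit to be placed in either class, but this is a clerical overlap between two illustrative examples, and its governing test lets sites grade a particular case sensibly. The effect on any estimate is nil as far as the protocol shows: the assessments lost at a visit are lost under both labels, and rewording would recover none of them. The TUG part does not hold, because omitting the test in a subject who cannot walk is permitted and is not a deviation. No bias in TUG change has been shown.

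This rests on two assumptions. The first is that the statistical analysis plan, which was not available, does not define an analysis set by major deviations; if it did, the class would begin to matter and that document would need its own definition. The second is that the case report forms, also not shown, allow a test to be marked as not done. The wording is worth tidying only if Section 8 is opened for another reason.
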